1.1 Breast Cancer Screening Today

Screening is testing of asymptomatic (without symptoms) and symptomatic women. Mammograms identify abnormalities and determine their location in the breast. If a biopsy of the area in question is positive, treatment includes surgical removal of the cancer followed by radiation and medical therapy, if indicated. The standard protocol in the United States for Breast Cancer screening includes an annual clinical breast exam and mammogram for women over 40 years of age². Women with a family history of Breast Cancer or other indicators may be screened at an earlier age and more frequently. If the results are positive, further diagnostic testing may be prescribed and a biopsy may be taken. If the SBSII scan reveals a thermal pattern on analysis that meets established criteria and the mammogram is read as normal, FSM intends to contact the site PI. The study participant will then be encouraged to undergo additional standard diagnostic imaging tests. These additional tests are performed to assure that the patient has no evidence of abnormality utilizing advanced breast imaging techniques in use today. However, the additional tests ordered may indicate the need for further investigation prescribed by the study doctor. These imaging tests will be paid for by First Sense Medical.

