1.3 Sentinel Breast Scan® System [SBSII]

The SBSII will automate the recording of thermal data used in the Therma-Scan manual thermology protocol by utilizing a thermal camera sensitive to changes in breast temperature. The SBSII system uses a very sensitive thermography camera that detects and visually displays heat patterns that naturally emanate from the breast. SBSII captures this data digitally for subsequent analysis by Therma-Scan.

This study will evaluate the clinical efficacy of the SBSII device in patients completing a screening or diagnostic mammogram. The thermal images captured on examination will be analyzed by Therma-Scan and the results will be compared to mammographic analysis. If the Sentinel Breast Scan II findings indicate a reading of either TH4 or TH5, FSM may request that the patient receive additional testing, ie breast ultrasound or MRI. The additional testing that are not considered routine and necessary based on standard breast imaging, will be paid for by the sponsor, as outlined in the study budget.

1.3.1 Projected Advantages of Sentinel Breast Scan® Test/Therma-Scan System:

1. **Higher sensitivity and positive predictive value (PPV)**, Sensitivity measures the percentage of positive results when cancer is present. PPV is the true positive rate, and is the percentage of abnormalities with a positive result. The false positive rate is the percentage of normals identified as abnormal. Higher positive sensitivity in a screened population is the goal of all screening methods. This parameter will be utilized in the analysis of data from this study.
2. On average, mammographic **sensitivity** varies between 60-90%. It is lower in women under age 40 and in those with dense breast tissue.
3. **Year-to-year comparisons.** An important factor in analysis is identification of subtle visual change that is detected by comparing a previous mammogram to a current one. SBSII® seeks to identify subtle changes over time in breast thermal signals through the use of sophisticated software.
4. **Patient Safety:** Practice guidelines in the United States delay screening younger women with mammography based on the accretion rate of radiation exposure. Thermographic analysis of the breast is radiation free and innocuous as a screening modality for younger women and is not affected by breast density.

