The core strengths of thermography are multi-faceted. Thermography is a fast, non-invasive, low cost and painless procedure performed without radiation exposure. Published studies support its use for early detection of breast tissue abnormalities and in identifying groups that may be at higher risk for developing breast cancer.

As an adjunct to mammography, thermography may be especially useful for screening younger, pre-menopausal women and women with dense breast tissue for whom mammography is less effective (Bleyer and Welch 2012).

³ Library, T.-S. R. (2011). "Thermology: Analytic Features." [A Professional's Guide To Breast Thermology](http://www.thermascan.com/professionals.html)
Retrieved January 4, 2013, from <http://www.thermascan.com/professionals.html>.

An automated platform for collecting thermal imaging data that provides objective, interpretative guidelines and standardized reporting would be an important adjunctive tool to aid in risk assessment and clinical decision-making in breast cancer screening.

Study Design and Selection and Exclusion of Subjects

1.4 Study Design: Testing a minimum of 2000 women receiving mammograms (comparing the SBSII/TS test results to the mammogram and biopsy results when applicable)

- a. SBSII test will be done before all mammograms, diagnostic or screening
- b. Women must wait a minimum of (3) days between mammography and the SBSII.
- c. If the SBSII test is positive and mammography is negative, FirstSense may request a breast ultrasound or MRI to determine the accuracy of SBSII. The acquisition order for MRI study will be done with prior approval by FSM.
- d. Any study subject, regardless of biopsy diagnosis and treatment, will continue to complete the SBS II imaging in conjunction with all future routine and necessary mammograms, not to exceed less than 6 months between each SBS II imaging, for up to 5 years from the start date of the subject's study participation. For subjects that undergo mastectomy after initial study participation, and are no longer completing routine and necessary mammograms, the SBS II will be completed with future routine and necessary breast MRI imaging, not to exceed less than 6 months between each SBS II imaging, for up to 5 years from the start date of the subject's study participation.

1.4.1 Subject Inclusion Criteria:

1. Female, over the age of 18 years of age.
2. Asymptomatic women or women who are being screened for breast abnormality.

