Thermal imaging data will be assessed by TS according to the internationally standardized thermology classification 'TH' scale, also known as the Marseilles system (Amalric, Brandone et al. 1978), which defines five categories of risk assessment.

The 3D, thermal and visible light data will be analyzed by TS to search for signs and criteria that indicate potential breast tissue abnormalities and arrive at a TH1-5 classification. Pattern recognition is used to identify blood vessels and measure the temperature points within these vessels. TS employs mathematical analysis to reduce the effective temperature variance and determine the probability of breast cancer. TS also uses mathematical techniques to measure magnitude of the focal areas on the breasts relative to the surrounding area. TS analyzes the average of approximately 10,000 data points and compares this analysis to the heat in any local hot spot. Sensitivity and specificity will be calculated by TS as described and data will be used to compare results with those from mammography and biopsy reports.

Clinically, a TH4-5 classification may result in a recommendation from the sponsor for further assessment. For study purposes, a comparison of the thermal categorization findings using the Marseille system to biopsy results will be analyzed. These results will provide a baseline for the semi-automated software analysis. Sensitivity and specificity will be calculated as follows:

TEST RESULT	CONDITION			Detection Rate
	Cancer	No Cancer	Total	
+ test	a (true positive)	b (false positive)	a+b	$\frac{a}{a+b}$ (positive predictive value=PPV)
- test	c (false negative)	d (true negative)	c+d	$\frac{d}{d+c}$ (negative predictive value=NPV)
Total	a+c	b+d	a+b+c+d	

\downarrow
 sensitivity = $\frac{a}{a+c}$

\downarrow
 specificity = $\frac{d}{b+d}$

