UADE (Unanticipated adverse device effects) Reporting:

1. Unanticipated adverse device effects (UADE) must be reported according to protocol, IRB and FDA requirements.
 - a. Verify that an evaluation of the UADE was completed and that risk determination to subjects has been made.
 - b. Verify that investigations presenting an unreasonable risk were terminated within 5 days of risk determination and fewer than 15 days after receiving notice of such effect.
 - c. Verify that an evaluation of the UADE, interventions, and outcome are described in the report.

- d. Verify that the UADE report was sent to the IRB (and FDA, where required) within the 10 working day time period and that copies of such correspondence are filed in the regulatory binder.
- e. Verify that a copy of the UADE report, IRB notification, IRB and FDA response are filed in the regulatory binder.

Follow Up:

- a. FSM may collect follow up information about study subjects if the study subject completes additional testing related to breast screening.

Regulatory Binder:

The regulatory binder will be checked at each visit to ensure that all required regulatory documents have been obtained prior to the start of the study and have been kept current during the study. They include:

- 1. Protocol and protocol amendments
- 2. Sample, approved Informed Consent form
- 3. CVs for investigators and sub-investigators, if applicable
- 4. Copies of current licenses and or certifications
- 5. Sample CRFs
- 6. Subject master log/Subject screening log
 - i. Must show documentation of existence/participation of subjects
 - ii. Must be consistent with information within the CRF and in the individual subject record.
- 7. Serious Adverse Event log
- 8. IRB approval
- 9. IRB composition
- 10. IRB correspondence
- 11. Signature log
- 12. Delegation of Authority log
- 13. Visitor log
 - i. Monitor will sign and date the log indicating:
 - ii. Date of the visit
 - iii. Name of the individual conducting visit
 - iv. Coordinator will confirm that visit took place by initialing.
- 14. Correspondence related to the study

Source Documents:

Source documents are essential documents that individually and collectively permit evaluation of the conduct of a clinical study and the quality of the data produced. Examples of source documents are hospital records, office charts, lab reports, x-rays, case report forms when date is entered directly, magnetic media, and photographic negatives.

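### Verification of SBSII-positive, mammogram-negative women is left to the device sponsor and follow-up collection is optional, so the accuracy figures in 1.6 are open to partial-verification bias of unknown size

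*Protocol*

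**What the plan says.** The Study Schema counts TH4 and TH5 as SBSII-positive and BIRADS 1 and 2 as mammogram-negative. For women with that combination, the protocol speaks in several places:

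- Section 1.4, item c: "FirstSense may request a breast ultrasound or MRI to determine the accuracy of SBSII". It adds: "The acquisition order for MRI study will be done with prior approval by FSM".
- Section 1.3, for any TH4 or TH5 reading: "FSM may request that the patient receive additional testing, ie breast ultrasound or MRI".
- Section 1.6: "Clinically, a TH4-5 classification may result in a recommendation from the sponsor for further assessment".
- Section 1.1 is firmer. Where the thermal criteria are met and the mammogram is normal, "FSM intends to contact the site PI. The study participant will then be encouraged to undergo additional standard diagnostic imaging tests", and "These imaging tests will be paid for by First Sense Medical".
- Section 1.4, item d: subjects "will continue to complete the SBS II imaging in conjunction with all future routine and necessary mammograms", for up to 5 years.
- Follow Up: "FSM may collect follow up information about study subjects if the study subject completes additional testing related to breast screening".

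Intended Use of the Data lists ancillary tests, biopsy and follow-up imaging among the comparators. The 1.6 table has only two condition columns, Cancer and No Cancer, and defines PPV as a/(a+b) and specificity as d/(b+d).

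**The concern.** Item c gives the purpose of the extra imaging as determining SBSII accuracy, so this is the step that supplies disease status for discordant positives. It is optional wherever the sponsor's request appears. The text at hand gives no rule for which women are imaged or with which test. The request is conditional on both results, so whoever makes it knows both. The fallback, later mammograms, may or may not be collected.

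A statistical analysis plan can say how unverified women are counted. It cannot recover a status that was never obtained, and it cannot undo selection whose basis was not recorded.

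What is at stake is the accuracy measurement under Specific Objective 2. Section 1.6 makes those results the baseline for the semi-automated software, and section 1.3.1 names higher PPV as a projected advantage.

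**Working it through.** The protocol states no expected PPV and no fraction to be verified, so there is no figure to reproduce. The following is an illustration.

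**Inputs from the protocol.** 2000 women (1.4); sensitivity 95% and specificity 91% for thermology (Introduction); mammographic sensitivity m = 60-90% (1.3.1).

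**Assumptions.**
- C = 20 or 100 cancers. The 100 is 10+45+45 from 1.6; those are upper limits and need not be filled from the first 2000 women.
- A share s = 80-90% of women without cancer is mammogram-negative.
- The two tests are independent given disease status.
- Every SBSII-positive, mammogram-positive woman gets a status.
- A completed ultrasound, MRI or follow-up mammogram settles status.
- A random fraction f of discordant positives is verified.

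**Cells.** TP = 0.95C, FP = 0.09(2000-C), TN = 0.91(2000-C).
- C = 20: 19, 178.2 and 1801.8; true PPV 19/197.2 = 9.6%.
- C = 100: 95, 171 and 1729; true PPV 95/266 = 35.7%.

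**Discordant positives.** TPd = TP(1-m) and FPd = s·FP. Their total is 144-192, or 55-85% of all SBSII positives.

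**Observed PPV.** a = TP-(1-f)TPd and b = FP-(1-f)FPd. If unverified women are dropped, PPV = a/(a+b). If they are filed as No Cancer, PPV = a/(TP+FP).

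| f | C=20, dropped | C=20, filed | C=100, dropped | C=100, filed |
|---|---|---|---|---|
| 25% | 15.7-23.3% | 6.7-8.9% | 49.3-61.3% | 25.0-33.0% |
| 50% | 12.4-15.6% | 7.7-9.2% | 42.6-49.0% | 28.6-33.9% |
| 75% | 10.7-11.8% | 8.7-9.4% | 38.5-41.1% | 32.1-34.8% |
| 90% | 10.0-10.4% | 9.2-9.5% | 36.7-37.7% | 34.3-35.4% |

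**Worked case** (C = 20, m = 0.8, s = 0.9, f = 0.5). TPd = 3.8, FPd = 160.4, a = 17.1, b = 98.0. Dropped: 17.1/115.1 = 14.9%. Filed: 17.1/197.2 = 8.7%.

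**Random verification can be corrected.** The concordant cells are 15.2 and 17.8; the verified discordant cells are 1.9 and 80.2. Weighting the latter by 1/f = 2 gives (15.2+3.8)/197.2 = 9.6%, the true value. The table therefore measures naive counting, not sponsor selection.

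**Selective verification cannot be corrected that way.** In the same case, suppose all 3.8 discordant cancers but only half of the 160.4 non-cancers are verified.
- Dropped: 19/(19+98.0) = 16.2%.
- Weighted by the overall fraction verified: that fraction is (3.8+80.2)/164.2 = 51.2%, so the estimate is (15.2+3.8/0.512)/197.2 = 11.5% against a true 9.6%.

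**Specificity, worked case, true 91.0%.**
- Unverified positives filed as No Cancer: 1801.8/(1801.8+178.2+1.9) = 90.9%.
- Unverified positives dropped, all SBSII-negative non-cancers kept: 1801.8/(1801.8+98.0) = 94.8%.
- Half of mammogram-negative women verified at random on both sides and the rest dropped: 0.55×1801.8 = 991.0, and 991.0/(991.0+98.0) = 91.0%.

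**The case against.** The strongest reply is that section 1.1 already sets out a default pathway for exactly these women: the sponsor means to contact the investigator, the woman is encouraged to have imaging, and the sponsor pays. On that reading the permissive wording elsewhere merely authorises non-routine scans. If the pathway is followed, f could be high, and at f = 90% even naive counting moves PPV by less than 1 point with 20 cancers. This stands as a limit on the likely size. It does not settle the matter, because section 1.1 states an intention and three other sections leave the step optional.

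Several further points hold in part:

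- The Follow Up wording may not reach the mammograms under item d. That is possible, but nothing else makes collection of those results routine.
- The schema diagram, an appendix and the study budget are not available, so a selection rule might exist outside the text at hand.
- Section 1.6 puts sensitivity and specificity first; PPV is a margin of its table.

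Stronger readings are tempting but unsupported. A reader might infer that the sponsor will pick cases to flatter the device, or that PPV must be overstated. The documents show that selection is possible, not that it is intended, and the direction depends on selection and on how unverified women are counted. A reader might also take the tabulated ranges as the cost of sponsor discretion; they assume random verification, which weighting would repair. Finally, a reader might infer that specificity would collapse. That needs every SBSII-negative, mammogram-negative woman to be discarded, which the protocol does not say; random half verification on both sides leaves it at 91.0%.

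**Conclusion.** The point holds as an open door to partial-verification bias. The protocol lets the device maker decide, knowing both results, which discordant positives receive a disease status, and it leaves the fallback data optional. PPV is directly affected; the effect on specificity has no fixed sign.

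The magnitude cannot be derived from the documents. Under the stated assumptions, more than half of all SBSII positives are discordant, so the discretion covers most of the PPV denominator. The numerical ranges only illustrate how far naive handling could move PPV at different values of f. Confidence is medium, because verification under the section 1.1 pathway could turn out nearly complete.

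Priority is modest: this is a feasibility study, and Intended Use of the Data restricts the results to device development, with no marketing submission.

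**What to change.** 1. Align section 1.4, item c and section 1.3 with section 1.1. Every woman with TH4-5 and BIRADS 1-2 is offered the sponsor-paid imaging already intended, under one rule and with the test named in advance. She may decline. MRI approval is given once for the rule, so there is no sponsor choice per woman. If the budget cannot cover all, offer imaging to a random fraction set in advance and weight verified discordant women by the inverse of that fraction.
2. Change the Follow Up paragraph to routine collection of the results of mammograms already expected under item d. Use them, within a window set in advance, to assign disease status to SBSII-positive and SBSII-negative women alike.
3. Keep every SBSII positive in the PPV denominator, report women still unresolved as unverified, and give worst-case and best-case bounds: a/(TP+FP) to [a+(1-f)(TPd+FPd)]/(TP+FP). In the worked case these are 17.1/197.2 = 8.7% to 99.2/197.2 = 50.3% with half resolved, and 18.62/197.2 = 9.4% to 35.04/197.2 = 17.8% with 90% resolved.

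**Cost.** The sponsor loses discretion and takes on some extra data collection. It may fund more of the imaging it already intends: with 20 cancers, offers would go to about 143-160 women without cancer (0.8 to 0.9 × 178.2) alongside 2-8 with cancer (19 × 0.1 to 0.4). Reported figures may be wider or less favourable. A random fraction lowers the imaging cost at the price of precision. No imaging beyond what section 1.1 already intends is asked for.

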1.2 Therma-Scan System

First Sense Medical® has partnered with Therma-Scan Reference laboratory, an established pioneer in medical thermology. Therma-Scan has been in operation for over 40 years and operates a diagnostic clinical imaging facility in Birmingham, Michigan. [name] has developed a complex and inclusive protocol for the detection of tissue abnormalities indicative of Breast Cancer. He has examined thermology scans on more than 500,000 women using a medical grade digital infrared camera

¹Hoekstra P, The autonomic challenge and analytic breast thermology. *Thermology International*, 2004(14);3:106.

²[American Cancer Society](#)

that utilizes advanced imaging techniques. [name] follows an analytic technique derived from the Marseille system to provide results of a breast thermogram on a recognized 'TH' scale.

Breast thermology is effective on women of all ages. And the density of breast tissue is not an impediment to breast thermal analysis. Utilization of the Marseille system, an internationally standardized thermology classification system, defines 5 TH categories based on a range of breast thermal findings; these range from TH-1, considered normal, thru TH-5, considered abnormal. Additionally, there are two other categories: TH-0, a technically defective test and TH-6, a known biopsy proven cancer. Therma-Scan Reference Laboratory will screen for thermal signs indicative of change and report the findings using this proven system.

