In addition, the data collected will be used to train, test and measure the accuracy of risk assessments utilized in manual thermography analysis when a cold air challenge is introduced into the clinical examination procedure. All data collected from study mammograms and biopsies will be divided into a phases consisting of all unblinded exams resulting in the identification of up to 10 biopsy proven cancer cases, a testing phase consisting of all double blinded exams resulting in the identification of up to 45 biopsy proven cancer cases, and a double blinded clinical trial consisting of all exams resulting in the identification of up to 45 biopsy proven cancer cases to measure the accuracy of manual thermography analysis as stated in Specific Objective 2.

1.7 Data analysis for Specific Objective 3:

The accuracy of the imaging system software to define the approximate location and identification of aberrant thermal signatures of increased metabolic activity will be compared to results found on analysis of mammographic and biopsy results.

IRB Ethics & Informed Consent:

The protocol, Informed Consent Form, and relevant supporting information must be submitted to the IRB for review and must be approved before the study is initiated. In addition, any subject recruitment materials must be approved by the IRB prior to use. This study will be conducted in accordance with the ethical principles that have their origin in the Declaration of Helsinki and that are consistent with the International Conference on Harmonization - Good Clinical Practice (ICH-GCP) guidance and applicable regulatory requirements. The study will be conducted in accordance with the regulations of the United States Food and Drug Administration (FDA) as described in 21 CFR Parts 50, 56 and relevant sections of 21 CFR Part 812, and the IRB requirements.

The sponsor must submit any change to the protocol to the IRB for review and approval before implementation. A protocol change intended to eliminate an apparent immediate hazard to subjects may be implemented immediately, provided the reviewing IRB is notified within 5 working days of implementation.

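### The laboratory whose readings are under test also calculates its own accuracy against biopsy, and the safeguards stated for the double blinded phases conceal identity, not outcome

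*Protocol*

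**What the plan says.** **Who reads.** Protocol section 1.6: "Thermal imaging data will be assessed by TS according to the internationally standardized thermology classification 'TH' scale". TS is to "arrive at a TH1-5 classification".

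**Who scores.** The same section: "Sensitivity and specificity will be calculated by TS as described", and in the same sentence, "data will be used to compare results with those from mammography and biopsy reports". The 2x2 table there cross-classifies test result by cancer status.

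**What is claimed about blinding.** Section 1.6 sets out an unblinded phase ending at no more than 10 biopsy-confirmed cancers, "a testing phase consisting of all double blinded exams" with a limit of 45, and a double blinded clinical trial, also with a limit of 45, which measures the accuracy of the manual reading. It does not say who is blinded to what.

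**What continues.** Section 1.4, item d: "Any study subject, regardless of biopsy diagnosis and treatment, will continue to complete the SBS II imaging", for up to 5 years.

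**What is protected.** Study Procedure, Table 2, Source Documents, Data Management and Confidentiality provide for coded identifiers and withhold names. Table 2 and Data Management put the study ID in the data file names. Data Management also says that TS employees have no access to the subject's ID.

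**TH-6.** Section 1.2 adds to the five graded categories "TH-0, a technically defective test and TH-6, a known biopsy proven cancer", and says TS will "report the findings using this proven system". The Study Schema lists TH-6 among SBS II results and counts it as negative.

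**The concern.** Blinding of a diagnostic reader means that the reading is final before the reader can learn the reference result. A laboratory can calculate its own accuracy afterwards without breaking that, but only if its reads are fixed first and it learns nothing that bears on scans still to be read. Here one party reads, receives cancer status, scores itself and carries on reading. Specific Objective 2 also allows the same TS method to be modified as well as measured, so TS has a development interest in the result.

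The last phase is the accuracy estimate for that objective, and section 1.6 makes the comparison with biopsy the baseline for the semi-automated software. If outcome knowledge reached the reads, both the estimate and the software built on it would be affected, and the final data would not reveal it.

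**Working it through.** The protocol gives no figure of its own on this point, so there is none to reproduce. The check is of roles and data flow, followed by an illustration of scale.

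**1. Does TS need outcomes?** Section 1.6 defines sensitivity = a/(a+c) and specificity = d/(b+d), where a and c are women with cancer and b and d women without. None of the four cells can be filled without cancer status. Assigning the calculation to TS therefore sends cancer status to TS.

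**2. Does any stated safeguard act on outcome?** Study Procedure keeps the link between name and identifier with the study staff and the PI. Table 2 appends the ID to the file names. Data Management and Confidentiality keep names from TS. All of these conceal identity. None withholds a mammogram or biopsy result, or says when a TH class becomes final.

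**3. Can knowledge carry forward?** The phases in section 1.6 are made up of exams, and the section does not say whether repeat exams count. Section 1.4, item d, generates repeat exams for up to 5 years, including after a biopsy diagnosis. A woman scored in one phase may thus be read again later. Whether TS could recognise her depends on the ID, and there the text conflicts: the ID is in the file names that TS receives, yet TS staff are said not to have it. TS also has to match reads to outcomes in order to score them, which needs some identifier.

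**4. TH-6.** The Study Schema and section 1.2 include it as a result; section 1.6 has TS assign TH-1 to TH-5. These do not agree.

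**5. Scale.** Input: 45 cancers, the upper limit for the final phase in section 1.6. The starting sensitivities and numbers of changed reads below are assumptions.

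- One missed cancer changed to positive: 1/45 = 2.2 points.
- Three changed: 3/45 = 6.7 points.

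| Start (exact 95% CI) | After three changed reads (exact 95% CI) |
|---|---|
| 34/45 = 75.6% (60.5 to 87.1) | 37/45 = 82.2% (67.9 to 92.0) |
| 40/45 = 88.9% (75.9 to 96.3) | 43/45 = 95.6% (84.9 to 99.5) |

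The shifts lie within the width of the intervals, but a confidence interval does not account for a systematic shift.

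**6. Direction of TH-6.** If k of the 45 cancers are coded TH-6 and counted negative, as the Study Schema has it, sensitivity becomes Se × (45 − k)/45.

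| Se of the other reads | k = 1 | k = 2 | k = 5 |
|---|---|---|---|
| 95% | 92.9% | 90.8% | 84.4% |
| 75% | 73.3% | 71.7% | 66.7% |

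This rule lowers sensitivity.

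**The case against.** Calculating after reading is compatible with blinding, and no text says TS receives outcomes before or during reading. A read lock or order of data release could sit in an SAP or reading manual that is not at hand. Data Management lists images, log files and completed CRFs as the stored data and does not list biopsy reports; the visible questionnaire has no outcome field, and the rest of the CRF cannot be checked. The study is a feasibility study for device development, not for a marketing submission.

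Much of this stands. It limits the point to a lack of protection rather than a demonstrated breach, and it lowers the stakes. It does not remove the point, because the assignment of scoring to TS and the claim of double blinding are both fixed in this protocol.

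Three stronger readings are tempting and are not supported:

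- *TS is told to assign TH-6, so its readers must know the biopsy.* Section 1.6 limits TS to TH-1 to TH-5, and a known cancer may mean a diagnosis disclosed before the scan. TH-6 is an inconsistency, not proof of unblinding. Because it counts as negative, it would not flatter the test.
- *Outcomes certainly follow women into later scans through the ID.* Data Management says TS employees lack the ID. That conflicts with the file naming, so the safeguard is unreliable as written, but the carry-over is not established.
- *The accuracy estimate will be inflated.* The documents give no basis for saying how many reads, if any, would be affected.

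**Conclusion.** The point holds in limited form. The protocol makes the party under test its own scorer, which gives it cancer status, and it claims double blinding while stating safeguards for identity only. The ID statements contradict each other, and the place of TH-6 differs between the Study Schema and section 1.2 on one side and section 1.6 on the other.

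The size of any bias cannot be derived. The 2.2 points per changed read assumes that the final phase reaches its upper limit of 45 cancers; with fewer, each read weighs more. The three-read examples show scale and are not a forecast. The change should be made: the estimate feeds software development and the remedy is cheap.

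**What to change.** In section 1.6, for the two double blinded phases:

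1. State who is blinded to what.
2. TS sends a dated, final TH class and location for each scan to the site staff, or to another non-TS party already in the study, before any mammogram or biopsy result for that woman can reach TS. The protocol does not show that the site staff hold the TH reads now, so this transfer has to be set up.
3. That party links the locked reads to the outcomes and computes the 2x2 table.
4. Sections 1.1 and 1.3 and section 1.4, item c, have the sponsor act on a positive scan with a negative mammogram. The results needed for that may go to the sponsor once the read is locked, but not to TS readers while the phase is open.
5. The accuracy set uses only scans read before TS could know that woman's outcome. Define this by the timing of the scan and not by its result, so that cancers and non-cancers are treated alike.
6. Reconcile TH-6 across the Study Schema and sections 1.2 and 1.6. State that it is not a category for blinded reads and is not counted as a negative test.
7. Reconcile the ID in the file names (Table 2, Source Documents, Data Management) with the statement that TS employees do not have it.

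Cost: protocol wording, one extra data transfer, and the table computed outside TS. TS receives feedback only when a phase closes.
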